### Handling Missing Data

- Multiple imputation for missing data assuming data are missing at random (MAR).
- Sensitivity analysis to validate robustness.

## Validation of Assumptions

1. **Normality:** Shapiro-Wilk test for residuals.
2. **Homogeneity of Variance:** Levene's test.
3. **Sphericity (if repeated measures):** Mauchly's test.

---

## Safety Analysis

- Descriptive statistics for adverse events (AEs) and serious adverse events (SAEs).
- AE rates compared using Fisher's exact test or chi-square test.

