### Study Protocol

#### Purpose

1. Demonstrate the clinical effectiveness of transcranial direct current stimulation (tDCS) for patients with depression in real-world clinical settings.
2. Optimize home-based electroceutical technologies for patient-centered applications.
3. Generate real-world data (RWD) and evidence (RWE) to support the adoption of tDCS in clinical practice.

---

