#### Design

##### 1. Overview:

- Randomized, double-blinded, multi-site clinical study.
- Participants: 198 adults aged 19–65 with mild to moderate major depressive disorder (MDD).
- Duration: 6 weeks of home-based self-applied tDCS.

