##### 3. Randomization:

- Group A: Active tDCS for 6 weeks.
- Group B: Active tDCS for 3 weeks followed by 3 weeks of sham stimulation.

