### Adjustments for Multiple Comparisons

To control for Type I error:

- Bonferroni correction for the analysis of multiple secondary outcomes.

---

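### The between-arm adverse event comparison is planned only as a significance test; for uncommon events at this sample size it needs a risk difference with a confidence interval

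*Combined protocol and SAP*

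**What the plan says.** The Safety Analysis section has two lines. The first plans "Descriptive statistics for adverse events (AEs) and serious adverse events (SAEs"). The second is the whole comparative plan: "AE rates compared using Fisher's exact test or chi-square test". The documents give no risk difference, risk ratio or confidence interval for this comparison. They also give no significance level, no expected event rate and no rule for reading the result.

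The arms are defined under Randomization as "Group A: Active tDCS for 6 weeks" and "Group B: Active tDCS for 3 weeks followed by 3 weeks of sham stimulation". The Overview sets the total at 198 patients; the allocation ratio is not stated. The multiplicity section provides only a "Bonferroni correction for the analysis of multiple secondary outcomes" and does not mention adverse events.

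**The concern.** A test of no difference answers only whether chance alone could explain the observed difference. A safety reader needs to know how large an excess of harm the data still allow. When events are uncommon and the arms are of moderate size, the test will often be non-significant even if the risk has doubled, and a p-value on its own does not show this. The risk is that a table of non-significant p-values is taken to mean that the two regimens are equally safe.

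The wording also leaves the test to be chosen later. Fisher's test is the more conservative of the two, so the same table can fall on either side of 0.05 depending on the choice.

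**Working it through.** **Inputs from the documents.** Total 198 patients (Overview). Two arms, both on active stimulation in weeks 1–3 (Randomization). Fisher or chi-square test (Safety Analysis). The plan states no safety power or precision figure, so there is none to reproduce.

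**Assumptions, because the documents are silent.** 1:1 allocation, so 198 / 2 = 99 per arm; no dropout, with 84 per arm (about 15% lost) as a sensitivity case; two-sided 5% level; a range of event rates; patients with at least one event as the unit.

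**1. Power for a doubled risk.** For each pair of true risks p and 2p, power is the sum, over all tables (x, y), of Bin(x; n, p) × Bin(y; n, 2p) for those tables where the test gives p ≤ 0.05. Chi-square is uncorrected.

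| True risks | Fisher, 99 per arm | Chi-square, 99 per arm | Fisher, 84 per arm | Chi-square, 84 per arm |
|---|---|---|---|---|
| 2% v 4% | 4% | 11% | 3% | 10% |
| 5% v 10% | 19% | 27% | 15% | 22% |
| 10% v 20% | 44% | 51% | 37% | 44% |
| 15% v 30% | 66% | 73% | 58% | 66% |
| 20% v 40% | 84% | 88% | 77% | 82% |

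At 99 per arm, power reaches 50% at a lower-arm rate of about 11% (Fisher) or 10% (chi-square), and 80% at about 19% or 17%. At 84 per arm the 50% points move to about 13% and 11%.

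**2. What the interval adds.** Suppose 10/99 v 5/99 patients have an event. Fisher gives p = 0.28. The risk difference is 0.1010 − 0.0505 = 0.0505. The Wilson limits are 0.0558 to 0.1760 for 10/99 and 0.0218 to 0.1128 for 5/99. The Newcombe interval is then:

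- lower: 0.0505 − √[(0.1010 − 0.0558)² + (0.1128 − 0.0505)²] = 0.0505 − 0.0770 = −0.026
- upper: 0.0505 + √[(0.1760 − 0.1010)² + (0.0505 − 0.0218)²] = 0.0505 + 0.0803 = 0.131

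So a result reported as not significant is compatible with anything from 2.6 points fewer to 13.1 points more patients with the event.

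**3. Choice of test.** Take 20/99 v 10/99. Fisher gives p = 0.073. For uncorrected chi-square the pooled risk is 30/198 = 0.1515, and z = 0.1010 / √(0.1515 × 0.8485 × 2/99) = 0.1010 / 0.0510 = 1.98, so p = 0.047. With the continuity correction the statistic is 198 × (990 − 99)² / (30 × 168 × 99 × 99) = 3.18, p = 0.074. The plan does not say which form is meant.

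**4. Zero events.** With no events in n patients, the exact one-sided 95% upper limit is 1 − 0.05^(1/n). For one arm, 1 − 0.05^(1/99) = 3.0%. All 198 patients are assigned at least 3 weeks of active stimulation, so for exposure to tDCS as such the pooled limit applies: 1 − 0.05^(1/198) = 1.5%.

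**The case against.** The strongest reply is that this is a reporting matter in a trial whose stated purposes do not include safety. The first purpose is "Demonstrate the clinical effectiveness of transcranial direct current stimulation (tDCS) for patients with depression in real-world clinical settings", and the other two concern home use and real-world evidence. A reader might infer that the plan intends to claim safety from a non-significant test. The documents do not support that: they contain no such claim and no interpretation rule. Descriptive AE and SAE statistics are already planned, and if these give patient counts per arm, anyone could work out an interval from them. This stands, and it limits the point to a gap in what is reported.

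It is also tempting to say that a doubled risk would usually be missed. That is not true in general. It holds for uncommon events, but power is 84% or 88% at 20% v 40%, and by chi-square it is marginally above one half at 10% v 20%. The documents give no expected rates, so the statement has to be conditional.

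Two further inferences should not be drawn. One is that repeated events from the same patient will be tested as if independent. The plan does not name the unit, but nothing in it prescribes event counts, and patients with at least one event is the ordinary reading. The other is that leaving AE tests outside the Bonferroni correction is an error. Unadjusted AE comparisons are common, correction would reduce power further, and the plan does not say that event types will be tested separately.

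Finally, both arms receive active stimulation in weeks 1–3. Neither a test nor an interval between arms can measure the harm of tDCS against no stimulation; it measures 6 against 3 active weeks. This stands too, and it governs how the interval must be labelled.

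What the reply does not remove is that the only comparative method named is a test without an estimate, and that the choice of test is open.

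**Conclusion.** The point holds as a reporting gap of moderate weight. At about 99 per arm, power for a doubled AE risk is at or below about 50% when the lower-arm rate is about 10% or less, and it is adequate only for common events. For uncommon events, a non-significant p-value therefore says little about the harm that remains possible, and it could be misread as comparable safety. The unspecified test can move a borderline table across 0.05.

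The conclusion rests on 1:1 allocation, a two-sided 5% level, no dropout and the patient as the unit. Dropout would lower power further. The documents do not show that the sponsor plans a safety claim from non-significance. No efficacy result, sample size or trial conduct is affected.

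**What to change.** Keep the descriptive statistics and replace the test line in the Safety Analysis section with wording to this effect:

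- For each AE type and for SAEs, report the number and percentage of patients with at least one event per arm, and the between-arm risk difference with a 95% confidence interval suited to small counts (for example Newcombe).
- Label that difference as 6 versus 3 weeks of active stimulation, not as tDCS versus no stimulation.
- Where no event occurs, give an exact upper limit: per arm, and pooled over all patients for exposure to tDCS (with 0/198, 1.5% one-sided).
- Name one test in advance, including whether a continuity correction is used if it is chi-square.
- Treat p-values as descriptive, and state that a non-significant result is not evidence of equal safety.

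The cost is SAP wording and a changed table layout; no new data or patients are needed. The one downside is that wide intervals will look less reassuring than a column of non-significant p-values.
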